9.8.2.3 Changes After Blind Break

Maximal VO₂ and VO₂ at VAT were summarized with units of mL/min in addition to the protocol-specified units of mL/kg/min. This was done since unchanged VO₂ in the presence of weight gain would cause VO₂ to appear to decrease when summarized as mL/kg/min.

Waterfall plots and cumulative distribution plots were generated for change from baseline to Week 26 in maximal VO₂ and VO₂ at VAT (mL/min and mL/kg/min).

Percent change from baseline was calculated for maximal VO₂ and VO₂ at VAT as the geometric mean ratio of the Week 26 minus baseline logarithm transformed exercise data.

An additional imputation method for missing data was included for exercise variables. When the Week 26 value was missing, the mean of non-missing Week 26 values (ignoring treatment group) was imputed.

For VO₂ at VAT, a linear regression model was also used to predict Week 26 VO₂ at VAT from Week 26 maximal VO₂. The predicted value from the model was used to impute VO₂ at VAT when maximal VO₂ was available; when maximal VO₂ was also missing, the average from all subjects with non-missing values was imputed.

Treatment-emergent abnormal laboratory tests were not identified on the basis of Grade III or Grade IV toxicity criteria from the National Cancer Institute Common Terminology Criteria. Shifts from within normal limits at baseline to above normal limits at Week 26 were summarized instead.

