11.4.1.1 Overview of Results for VO_2 at VAT and Maximal VO_2

For the protocol-specified primary endpoint, the udenafil group had a mean increase from baseline to Week 26 in maximal VO_2 (44.40 mL/min) compared to a mean decrease in the placebo group (-3.65 mL/min). The least squares mean treatment group difference for change from baseline to Week 26 in maximal VO_2 was 41.04 mL/min ($p=0.071$). When standardized by each subject's body weight, the least squares mean treatment group difference was 0.64 mL/kg/min ($p=0.092$). Results were consistent across methods of imputation for missing data and analysis populations ([Table 12](#)).

For VO_2 at VAT, the udenafil group had a mean increase from baseline to Week 26 in VO_2 at VAT (29.65 mL/min) as compared to a mean decrease in the placebo group (-8.01 mL/min). The least squares mean treatment group difference for change from baseline to Week 26 in VO_2 at VAT was 41.58 mL/min ($p=0.023$). When standardized by each subject's body weight,

the least squares mean treatment group difference was 0.78 mL/kg/min (p=0.012). Results were consistent across methods of imputation for missing data and analysis populations (Table 12).

Table 12: Overview of Analyses of Change Between Week 26 and Baseline Visits for Maximal VO₂ and VO₂ at VAT

VO ₂ Measure (units) Endpoint, Population, Imputation	Mean (Standard Deviation)		Difference	
	Udenafil	Placebo	LS Mean (SE)	p-value ^a
Maximal VO₂ (mL/kg/min)				
Change, ITT, LOCF	-0.23 (4.056)	-0.89 (3.672)	0.64 (0.377)	0.092
Maximal VO₂ (mL/min)				
Change, ITT, LOCF	44.40 (238.291)	-3.65 (222.417)	41.04 (22.709)	0.071
Change, ITT, OC	46.98 (244.914)	-3.84 (228.224)	44.68 (23.897)	0.062
Change, ITT, mean of non-missing ^b	60.68 (261.742)	-1.34 (235.417)	51.72 (24.090)	0.032
Change, PP, LOCF	42.23 (238.652)	6.17 (207.286)	31.40 (22.363)	0.161
LN (change), ITT, LOCF	0.03 (0.163)	-0.01 (0.195)	0.03 (0.018)	0.070
LN (change), ITT, OC	0.03 (0.168)	-0.01 (0.200)	0.04 (0.019)	0.061
LN (change), ITT, mean of non-missing ^b	0.04 (0.184)	-0.01 (0.202)	0.04 (0.019)	0.033
LN (change), PP, LOCF	0.03 (0.163)	0.00 (0.134)	0.02 (0.015)	0.176
VO₂ at VAT (mL/kg/min)				
Change, ITT, LOCF	-0.07 (2.998)	-0.68 (3.216)	0.78 (0.308)	0.012
VO₂ at VAT (mL/min)				
Change, ITT, LOCF	29.65 (177.023)	-8.01 (183.031)	41.58 (18.224)	0.023
Change, ITT, OC	32.52 (185.191)	-8.95 (193.508)	50.56 (20.074)	0.012
Change, ITT, mean of non-missing ^b	42.12 (185.414)	-10.81 (204.340)	58.31 (19.040)	0.002

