Change, ITT, linear regression	37.66 (189.688)	-15.93 (204.787)	58.83 (19.403)	0.003
Change, PP, LOCF	27.95 (176.397)	-2.78 (175.846)	38.62 (17.945)	0.032
LN (change), ITT, LOCF	0.03 (0.168)	-0.02 (0.252)	0.05 (0.022)	0.024
LN (change), ITT, OC	0.03 (0.176)	-0.02 (0.267)	0.06 (0.025)	0.015
LN (change), ITT, mean of non-missing ^b	0.05 (0.180)	-0.02 (0.266)	0.07 (0.023)	0.005
LN (change), ITT, linear regression	0.04 (0.186)	-0.03 (0.268)	0.07 (0.023)	0.005
LN (change), PP, LOCF	0.03 (0.167)	0.00 (0.184)	0.04 (0.018)	0.028

ANCOVA=analysis of covariance; ITT=intent-to-treat; LOCF=last observation carried forward; LN=natural logarithm; LS=least squares; OC=observed cases; PP=per protocol; SE=standard error; VAT=ventilatory anaerobic threshold; VO₂=minute oxygen consumption

a P-value was assessed using ANCOVA with fixed factors for ventricular morphology (single left versus single right or mixed) and treatment group with a continuous covariate of baseline maximal VO₂.

b When the Week 26 value was missing, the mean of non-missing Week 26 values (ignoring treatment group) was imputed.

Source: Table 14.2.1.1.1, Table 14.2.1.1.2, Table 14.2.1.1.3, Table 14.2.1.1.4, Table 14.2.1.2.1, Table 14.2.1.2.2, Table 14.2.1.2.3, Table 14.2.1.2.4, Table 14.2.2.1.1, Table 14.2.3.1.1, Table 14.2.3.1.2, Table 14.2.3.1.3, Table 14.2.3.1.4, Table 14.2.3.1.5, Table 14.2.3.2.1, Table 14.2.3.2.2, Table 14.2.3.2.3, Table 14.2.3.2.4, Table 14.2.3.2.5, and Table 14.2.4.1.1

Program: T_14_2_1_1.sas, T_14_2_1_1_2.sas, T_14_2_1_1_3.sas, T_14_2_1_1_4.sas, T_14_2_1_2_1.sas, T_14_2_1_2_2.sas, T_14_2_1_2_3.sas, T_14_2_1_2_4.sas, T_14_2_2_1_1.sas, T_14_2_3_1_1.sas, T_14_2_3_1_2.sas, T_14_2_3_1_3.sas, T_14_2_3_1_4.sas, T_14_2_3_1_5.sas, T_14_2_3_2_1.sas, T_14_2_3_2_2.sas, T_14_2_3_2_3.sas, T_14_2_3_2_4.sas, T_14_2_3_2_5.sas, and T_14_2_4_1_1.sas

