Results for treatment group differences in change from baseline in maximal VO_2 using units of mL/min were generally similar for analyses using no imputation ($p=0.062$, [Table 14.2.1.1.2](#)), imputation with the mean of non-missing values at Week 26 ($p=0.032$, [Table 14.2.1.1.3](#)), and last observation carried forward (LOCF) for Per Protocol population ($p=0.161$, [Table 14.2.1.1.4](#)). Analysis of ranked changes using LOCF ([Table 14.2.1.1.5](#)) and imputation with zero ([Table 14.2.1.1.6](#)) demonstrated $p<0.05$ for treatment differences ($p=0.026$ and $p=0.045$, respectively).

Results for treatment group differences in change from baseline in maximal VO_2 using units of mL/kg/min were generally similar for analyses using no imputation ($p=0.089$, [Table 14.2.2.1.2](#)), imputation with the mean of non-missing values at Week 26 ($p=0.083$, [Table 14.2.2.1.3](#)), LOCF for Per Protocol population ($p=0.188$, [Table 14.2.2.1.4](#)), ranked changes ($p=0.069$, [Table 14.2.2.1.5](#)), and imputation with zero ($p=0.422$, [Table 14.2.2.1.6](#)).

Waterfall plots for change in maximal VO_2 from baseline to Week 26 are presented in [Figure 14.2.1.1.3](#) for units of mL/min and in [Figure 14.2.1.1.4](#) for units of mL/kg/min. The cumulative distribution curve for change in maximal VO_2 from baseline to Week 26 is presented in [Figure 14.2.1.1.5](#) for units of mL/kg/min. For these figures, no imputation was performed for missing observations.

The udenafil group had a mean increase from baseline to Week 26 in the natural logarithm of maximal VO_2 (0.03) compared to a mean decrease in the placebo group (-0.01). The least squares mean treatment group difference for change from baseline to Week 26 in the natural logarithm of maximal VO_2 was 0.03 ($p=0.070$). Change from baseline to Week 26 in maximal VO_2 (displayed as natural logarithms of mL/min and mL/kg/min) is summarized in [Table 14](#).

Table 14: Change in the Natural Logarithm of Maximal VO₂ Between Week 26 and Baseline Visits Using Last Observation Carried Forward (ITT Population)

Endpoint (units) Statistic	Udenafil (N=200)	Placebo (N=200)	Difference LS Mean (SE)	p-value
Maximal VO₂ (natural logarithm of mL/min)				
Baseline, mean (SD)	7.32 (0.280)	7.36 (0.251)	-0.05 (0.027)	0.075 ^a
Week 26, mean (SD)	7.34 (0.276)	7.35 (0.301)	-0.01 (0.029)	0.765 ^a
Change from baseline				
Mean (SD)	0.03 (0.163)	-0.01 (0.195)	0.03 (0.018)	0.070 ^b
Median	0.02	0.00		

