11.4.2 Statistical/Analytical Issues

11.4.2.1 Adjustments for Covariates

The primary efficacy endpoint (aerobic exercise performance) and some of the secondary efficacy endpoints were analyzed with an ANCOVA model with fixed factors for ventricular morphology and treatment groups with a covariate of the relevant baseline value.

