11.4.2.2 Handling of Dropouts or Missing Data

The following imputation method was used for the primary analysis of the primary outcome:

- Subjects who died or dropped out of the study with unknown vital status were to be assigned a maximal VO_2 of zero at Week 26. No subject met this criterion.
- Subjects who were known to be alive, but who discontinued from the study (and were missing maximal VO_2 at Week 26) were assigned the latest value available.

- Subjects who completed Week 26 but were physically unable to reach maximum effort in cardiopulmonary exercise testing after 2 attempts, were assigned their baseline value (ie, zero change).

Two additional sensitivity analyses to assess the impact of missing data were conducted as follows:

- Subjects with missing maximal VO₂ at Week 26 were assigned a maximal VO₂ of zero.
- Subjects with missing maximal VO₂ at Week 26 were excluded from analysis (ie, observed cases analysis).

An additional imputation method for missing data was included for exercise variables. When the Week 26 value was missing, the mean of non-missing Week 26 values (ignoring treatment group) was imputed.

For VO₂ at VAT, a linear regression model was used to predict Week 26 VO₂ at VAT from Week 26 maximal VO₂. The predicted value from the model was used to impute VO₂ at VAT when maximal VO₂ was available; when maximal VO₂ was also missing, the average from all subjects with non-missing values was imputed.

Missing item scores for rating scales were imputed according to published methodology for the scale. Otherwise, missing data were not estimated for secondary efficacy endpoints.

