The protocol-specified primary endpoint of maximal VO₂ measures overall aerobic capacity and has been shown to be useful as a predictor of cardiac death and hospitalization for heart failure, both in congenital and acquired heart disease. Given the relative ease of obtaining this measure and its utility as a surrogate outcome, maximal VO₂ has been chosen as an endpoint in multiple observational studies and clinical trials. In view of the above, and to be consistent with generally accepted understanding in the pediatric cardiology community, maximal VO₂ was chosen as the primary endpoint for the FUEL trial. An alternative exercise measure, VO₂ at VAT, was also considered during the initial study design, but was designated as a secondary endpoint for 2 reasons: 1) There were more limited relevant data from prior studies to allow for a robust power calculation, and 2) VO₂ at VAT is more difficult to measure precisely, which could lead to data loss and impact statistical power in this rare pediatric disease. The concern about data loss was confirmed in the FUEL trial in which 21% of participants did not have paired data VO₂ at VAT ([Table 14.2.3.1.2](#)) versus 5% for maximal VO₂ ([Table 14.2.1.1.2](#)).

Despite its utility in most forms of heart disease, recent publications suggest that maximal VO₂ may not be an ideal efficacy measure for interventions in Fontan physiology, particularly for therapies that would improve exercise performance by modification of the PVR. During

exercise, there is a substantial increase in metabolic demand for oxygen delivery and, therefore, cardiac output. In the absence of a sub-pulmonary pump, preload is maintained by the pressure gradient across the pulmonary vascular bed; the difference between CVP and atrial pressure. As exercise intensity increases, CVP must rise to allow for increased transpulmonary blood flow (Qp). Udenafil may modulate this relationship by lowering PVR and therefore allowing for a lower CVP for any given amount of Qp. However, as exercise intensity increases, modification of PVR alone may not be sufficient to allow for the needed increase in cardiac output. Even with optimal pulmonary vasodilation, an increase in CVP is required to provide adequate Qp to keep up with metabolic demand. At the highest levels of exertion, one begins to exceed the physiologic limit of maximal CVP. This physiologic limit, or ceiling, is that point at which exercise is limited by an inability to raise CVP any further.

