6.4.3 Missing Data

The following imputation method will be used for the primary analysis of the primary outcome:

- Subjects who have died or have dropped out of the study with unknown vital status will be assigned a maximal VO₂ of zero at Visit 4.
- Subjects who are known to be alive, but who discontinued from the study (and are missing maximal VO₂ at Visit 4) will be assigned the latest value available (e.g., value from end of study visit if available, and from baseline visit otherwise).
- Subjects who complete Visit 4, but are physically unable to reach maximum effort in cardiopulmonary exercise testing after two attempts, will be assigned their baseline value (i.e., zero change).

Two additional analyses to assess the impact of missing data will be conducted as follows:

- Subjects with missing maximal VO₂ at Visit 4 will be assigned a maximal VO₂ of zero
- Subjects with missing maximal VO₂ at Visit 4 will be excluded from analysis (i.e., observed cases analysis).

Missing item scores for rating scales will be imputed according to published methodology for the scale. Otherwise, missing data will not be estimated for secondary efficacy endpoints.

CONFIDENTIAL

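### The pooled Week 26 mean imputation, added after unblinding, ignores each subject's own baseline and should not count as robustness evidence for maximal VO₂ in mL/min

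*Protocol*

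**What the plan says.** SAP 6.4.3 sets the primary rule for missing maximal VO₂: zero for death or unknown vital status, the latest available value for other dropouts, and zero change if maximal effort cannot be reached. It then states "Two additional analyses to assess the impact of missing data will be conducted as follows" and names zero imputation and observed cases.

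Protocol section 9.8.2.3 adds a further rule after blind break: "When the Week 26 value was missing, the mean of non-missing Week 26 values (ignoring treatment group) was imputed". The same section lists the mL/min units, the log-scale (percent change) analysis and the regression imputation for VO₂ at VAT as post-unblinding additions. It names mL/kg/min as the protocol-specified unit.

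Section 11.4.2.2 introduces the rule with "An additional imputation method for missing data was included for exercise variables" and gives no timing. Footnote b of Table 12 describes the rule, also without timing. Section 11.4.1.1 says of maximal VO₂: "Results were consistent across methods of imputation for missing data and analysis populations". Section 11.4.2.1 describes the analysis model as an ANCOVA "with a covariate of the relevant baseline value".

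**The concern.** Under this rule the imputed change is a constant minus the subject's own baseline. A subject with a low baseline and no Week 26 test is credited with a large gain, although the trial's own model treats baseline as informative. If the missing subjects in one arm started lower than those in the other, the rule turns that imbalance into an apparent treatment effect without any Week 26 measurement behind it.

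The rule supplies the only two maximal VO₂ rows below 0.05 in Table 12: 0.032, and 0.033 on the log scale. They stand beside planned methods with no mark of when they were added, and the text counts them as agreeing with the rest. What is at stake is the sensitivity evidence and how it is described.

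**Working it through.** **Inputs** (maximal VO₂, mL/min, ITT, udenafil then placebo).
- Table 12, mean change (SD): LOCF 44.40 (238.291), -3.65 (222.417). Observed cases 46.98 (244.914), -3.84 (228.224). Pooled mean 60.68 (261.742), -1.34 (235.417).
- Table 13: baseline 1562.00 (437.329), 1626.95 (413.992). Week 26 LOCF 1606.40 (451.719), 1623.30 (432.153).

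**1. Published p-values.** 44.68/23.897 = 1.870 gives p=0.062. 51.72/24.090 = 2.147 gives p=0.032. 41.04/22.709 = 1.807 gives p=0.071. All three reproduce.

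**2. Number missing.** If carried-forward subjects have zero change, n observed = 200 × LOCF mean / observed-case mean.
- Udenafil: 200 × 44.40/46.98 = 189.0, so 11 missing.
- Placebo: 200 × 3.65/3.84 = 190.1, so 10 missing.
- Total: 21/400 = 5.25%, matching "versus 5% for maximal VO₂" in section 11.4.7.
- Setting those 21 changes to zero also returns the published LOCF SDs, 238.291 and 222.417.

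**3. Change credited by the rule.**
- Udenafil: 200 × (60.68 - 44.40)/11 = 3,256/11 = +296.0.
- Placebo: 200 × (-1.34 + 3.65)/10 = 462/10 = +46.2.
- Imputed constant: (200 × 1606.40 + 200 × 1623.30 + 3,256 + 462)/400 = 1,624.1.

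**4. Baselines of the missing subjects.**
- Udenafil: 1,624.1 - 296.0 = 1,328.1, which is 233.9 below 1562.00. The implied SD of 414 gives SE 414/√11 = 125.
- Placebo: 1,624.1 - 46.2 = 1,577.9, which is 49.0 below 1626.95. The implied SD of 359 gives SE 359/√10 = 114.

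**5. Change that the baselines support.** The pooled slope of change on baseline from Table 13 is the sum over arms of (Week 26 variance - baseline variance - change variance)/2, divided by the sum of baseline variances: -39,046/362,646 = -0.108. In observed cases it is -0.115, with baseline means 1575.6 and 1629.5.
- Udenafil: 46.98 - 0.115 × (1328.1 - 1575.6) = about +75, against +296 credited.
- Placebo: -3.84 - 0.115 × (1577.9 - 1629.5) = about +2, against +46 credited.

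**6. ANCOVA rebuilt from these moments** (arm and baseline; morphology omitted because its moments are not published). Adjusted difference = raw difference - slope × baseline difference.

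| Analysis | Calculation | Rebuilt (SE, p) | Published (SE, p) |
|---|---|---|---|
| LOCF | 48.05 - 0.108 × 64.95 | 41.06 (22.68, 0.071) | 41.04 (22.709, 0.071) |
| Observed cases | 50.83 - 0.115 × 53.92 | 44.63 (23.87, 0.062) | 44.68 (23.897, 0.062) |
| Pooled mean | 62.02 - 0.158 × 64.95 | 51.74 (24.06, 0.032) | 51.72 (24.090, 0.032) |

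The published shift is 51.72 - 44.68 = 7.04 (0.29 SE) from observed cases and 51.72 - 41.04 = 10.68 (0.47 SE) from LOCF.

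**7. Same rule, observed data fixed, only the missing subjects' baselines moved.**
- Both arms' missing subjects at their arm means: 43.4 (SE 23.79, p=0.069).
- Only the udenafil ones at 1562.00: 41.3 (SE 23.79, p=0.083).
- Udenafil ones 234 above their arm mean: 30.1 (SE 23.96, p=0.21).

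**8. Protocol-specified unit.** In mL/kg/min, sections 11.4.1.1 and 11.4.1.2 give p=0.083 (pooled mean), 0.089 (observed cases) and 0.092 (LOCF). On the log scale of mL/kg/min the pooled mean gives 0.075, against 0.073 with no imputation.

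**The case against.** The strongest reply is that nothing is hidden and little depends on the row. Section 9.8.2.3 states both rule and timing, footnote b states the rule, and section 11.4.1.2 prints every p-value, including 0.161 for the Per Protocol population. The efficacy conclusions quote only 0.071 and 0.092 for maximal VO₂ and concede that the primary endpoint missed significance. All of that stands. It limits the fault to Table 12, section 11.4.2.2 and the claim of consistency.

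The rule also ignores treatment group and does not inherently favour udenafil. With missing subjects at their arm means it gives a slightly smaller difference than observed cases. That stands too. A reader might infer that the rule was picked because it favoured udenafil, or that low-baseline udenafil subjects dropped out selectively. The documents support neither: the shortfall rests on 11 subjects with SE about 125.

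The SAP's zero imputation likewise sets change to a constant minus own baseline, and its ranked version gives 0.045 in mL/min. So ignoring baseline alone does not disqualify a method. Zero imputation was planned before unblinding, whereas the pooled-mean rule was not.

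Finally, estimates of 31 to 52 mL/min with SE near 23 all share a sign and may be called consistent in direction. That is fair, but the wording does not tell the reader that the result below 0.05 comes from an unplanned rule.

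**Conclusion.** The point holds for maximal VO₂ in mL/min. The move from p=0.062 to p=0.032 comes from where 21 unmeasured subjects started, mainly the 11 on udenafil. It is not extra evidence that the result is robust.

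The counts and baselines are derived, on the assumption that carried-forward subjects have zero change; the near-integer counts and the exact SD match support this. The rebuilt model omits morphology but agrees with all three published rows to within 0.06 mL/min. The log-scale row (0.033) was not rebuilt; it uses the same rule on the same mL/min data.

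Three stronger readings should be resisted:
- The primary result is not affected. LOCF is not significant in either unit (0.092 in mL/kg/min, 0.071 in mL/min) and does not use this rule.
- The pooled-mean rows are not the only post hoc ones. Every mL/min and log-scale row in Table 12 was added after unblinding.
- No inflation of VO₂ at VAT is shown. Its observed-case result in mL/min is already p=0.012, and no size of bias is claimed there.

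**What to change.** 1. Do not count the pooled-mean maximal VO₂ rows (0.032, and 0.033 on the log scale) as robustness evidence. They can stay in the table.
2. In Table 12 and section 11.4.2.2, mark everything added after blind break: mL/min units, log scale, pooled mean and VAT regression imputation. Note that the pooled-mean rule ignores own baseline. The VAT rows need only the post hoc label.
3. Rest robustness first on the SAP analyses in mL/kg/min: LOCF 0.092, observed cases 0.089, Per Protocol 0.188, ranked 0.069, ranked zero imputation 0.422. Then give the same analyses in mL/min, labelled post hoc: 0.071, 0.062, 0.161, 0.026 and 0.045.
4. In section 11.4.1.1, for maximal VO₂, replace "Results were consistent across methods of imputation for missing data and analysis populations" with these p-values.
5. If a further imputation is wanted, use multiple imputation conditional on arm, own baseline and ventricular morphology, labelled post hoc. Avoid a single predicted value per subject, because it understates the SE: about 22.6 against 23.9 in observed cases. In the rebuilt model it gives 44.6, p=0.049 with arm in the prediction, and 42.4, p=0.062 without.

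The cost is labels on table rows, a phrase in section 11.4.2.2 and one reworded sentence. No re-run is needed unless the optional imputation is done. Two favourable p-values stop counting as support.

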9.8.2.4 Changes to Address Refusal to File Letter

The MedDRA coding of some adverse events was revised for consistency per request by the Food and Drug Administration.

The definition of TEAEs was changed from events that began after receipt of randomized study drug to events that began after receipt of randomized study drug and within 90 days after last dose of study drug.

10 Study Subjects

